COVID-19	Coronavirus disease 2019, caused by severe acute respiratory syndrome coronavirus 2 (SARS-CoV-2)
CRF	case report form
CS	clinically significant
CTCAE	Common Terminology Criteria for Adverse Events
D	study day
DGP	deamidated gliadin peptides
DLT	dose limiting toxicity
EAE	experimental autoimmune encephalomyelitis
ECG	electrocardiogram
eCRF	electronic case report form
CCI	
Early Term	early termination
FIH	first in human
GC	gluten challenge
GCP	Good Clinical Practice
GFD	gluten-free diet
GI	gastrointestinal
GLP	Good Laboratory Practice
HBsAg	hepatitis B surface antigen
HBV	hepatitis B
HCV	hepatitis C

Acronym / Abbreviation	Definition
HIV	human immunodeficiency virus
HLA	Human Leukocyte Antigen
IBS	Irritable bowel syndrome
ICF	informed consent form
ICH	International Conference on Harmonisation
IEC	Independent Ethics Committee
CCI	[REDACTED]
IgA	immunoglobulin A
IgG	immunoglobulin G
IRB	Institutional Review Board
IRR	infusion-related reaction
IRT	interactive response technology
ITT	intention-to-treat
IV	intravenous
Ig	immunoglobulin
IgA	immunoglobulin A
IgG	immunoglobulin G
LEC	Local Ethics Committee
MAD	multiple ascending dose
MBBS	Bachelor of Medicine
MedDRA	Medical Dictionary for Regulatory Activities
MHC	major histocompatibility complex
MTD	maximum tolerated dose
NCI-CTCAE	National Cancer Institute Common Terminology Criteria for Adverse Events
NOAEL	no observed adverse effect level
NTD	non-tolerated dose
CCI	[REDACTED]
PBO	placebo
PD	pharmacodynamic(s)
PE	physical examination
PK	pharmacokinetics

Acronym / Abbreviation	Definition
PLT	platelet
PO	orally
CCI	[REDACTED]
SAD	single ascending dose
SAE	serious adverse event
SAP	statistical analysis plan
SARS-CoV-2	severe acute respiratory syndrome coronavirus 2
SMC	Study Monitoring Committee
StD	standard deviation
TEAE	treatment-emergent adverse event
tTG	tissue transglutaminase
ULN	upper limit of normal
WBC	White blood cell
WCBP	women of child-bearing potential

1. BACKGROUND

1.1. Celiac Disease

Celiac disease (CeD) is an inherited autoimmune disorder that affects the digestive process of the small intestine. When a patient with CeD consumes gluten, that individual's immune system responds by attacking the small intestine, thereby inhibiting the absorption of nutrients. CeD can present with a variety of gastrointestinal (GI) symptoms, include diarrhea, bloating, flatulence and abdominal pain, and non-GI symptoms such as anemia and vitamin deficiencies (Halfdanarson 2007, Rubio-Tapia 2013). Undiagnosed and untreated CeD has been linked to the development of other autoimmune disorders, nutritional disorders such as osteoporosis and infertility, and neurological conditions (Green 2006, Green 2001).

It has been recently estimated that 0.7% of the world-wide population has CeD, with global prevalence rates on the rise (Singh 2018). CeD is strongly associated with the Human Leukocyte Antigen (*HLA*)-*DQA1* and *HLA-DQB1* loci (*HLA-I*05*, *HAL-DQB1*02*; commonly referred to as HLA-DQ2.5) which is present in approximately 90% of CeD patients (Sollid 1989, Sollid 2012). The pathology observed in CeD patients is driven by the adaptive immune response specific to proteins generated in the digestive system after ingestion of gluten, which results in autoimmune-like pathology in the small intestine (Sollid 2013). Diagnosis is typically made by a combination of positive immunoglobulin A (IgA) anti-tissue transglutaminase (TTG) and/or immunoglobulin G (IgG) anti-deamidated gliadin peptides (DGPs) and small intestinal biopsy demonstrating villous abnormalities while on a gluten-containing diet or following a GC (Halfdanarson 2007, Rubio-Tapia 2013).

There is currently no pharmaceutical treatment approved for the management of CeD. Patients manage their symptoms by strict adherence to a gluten-free diet (GFD), which often presents a substantial logistical and financial burden (See 2015). The effectiveness of the GFD is limited not only by motivation, access, and expense, but by uncertainty related to potential gluten content of certain medications and supplements. Adherence to the strict GFD is also limited by the ubiquity of gluten contamination in many gluten-free foods. Several studies have shown incomplete histological normalization of small bowel mucosa despite a strict GFD, with persistent villous atrophy seen in up to 79% of treated patients (See 2015). In addition to adherence challenges, some patients report persistent, life-affecting symptoms despite attempting to adhere to the GFD. Patients with CeD who adhere to a strict GFD continue to have a heavy burden of care.

Thus, there remains a strong unmet medical need for pharmacologic interventions to help alleviate the growing disease burden of CeD.

1.2. KAN-101

KAN-101 is composed of a synthetic liver-targeting glycopolymer that is conjugated to a synthetic **CC1** peptide domain of wheat alpha gliadin (KAN0009) recognized by the HLA-DQ2.5 haplotype. KAN0009 does not bind to the HLA DQ8 molecule. KAN-101 is a liquid formulation drug product administered parenterally via an intravenous (IV) infusion.

KAN-101 harnesses natural tolerogenic pathways in the liver (Thomson 2010) to reprogram pathogenic immune cells to become tolerant toward specific antigens. KAN-101 specifically targets the immune cells that drive CeD and leaves the otherwise healthy components of the immune system intact to perform their natural, protective functions. The mechanism by which KAN-101 induces immunologic tolerance is mediated by 3 mechanisms:

- Deletion of antigen-specific T cells
- Induction of anergy/clonal exhaustion of antigen-specific T cells
- Induction of regulatory T cells which control the antigen-specific T-cell response

In nonclinical mouse models and a non-human primate model, administration of surrogate molecules of KAN-101 were effective at inducing T-cell tolerance. From these nonclinical models, it was concluded:

- Three doses of surrogate molecules administered every 3 days was significantly more effective in inducing tolerance and improving disease outcome compared to 3 doses administered weekly.
- The doses where optimal efficacy was observed for the surrogate molecules in nonclinical models is equivalent to 1.5 to 7.0 mg/kg of KAN-101. Doses of surrogate molecules equivalent to 0.3 mg/kg of KAN-101 have demonstrated effects on disease severity in nonclinical models.
- T-cell tolerance induction can be observed as early as 1 week after drug administration in nonclinical models, supporting the observational period for the dosing of the sentinel patients across cohorts.

Previous clinical studies using an adjuvant-free mix of 3 peptides were able to induce T-cell tolerance in patients with CeD (Goel 2017). Intradermal administration of these non-targeted peptides induced moderate celiac-like GI symptoms in some patients, including nausea, abdominal pain, and vomiting, with onset within hours of drug administration. In general, these symptoms are consistent with symptoms experienced by CeD patients after ingestion of gluten (Goel 2017).

For more information on the nonclinical findings, please see the KAN-101 Investigator's Brochure.

Based on the nonclinical findings, Kanyos is initiating this first-in-human (FIH) study with KAN-101 in patients with CeD.

1.3. Selection of Patient Populations

The study population includes adults with CeD based on intestinal histology showing villous atrophy at the time of diagnosis and a record of positive serology (tTG-IgA and/or DGP-IgG). In addition, eligible patients must have HLA-DQ2.5 genotype (HLA-*DQA1**05 and HLA-*DQB1**02) (homozygotes or heterozygotes) since the KAN0009 peptide will bind this major histocompatibility complex (MHC) molecule. Patients who are positive for HLA-DQ8 (*DQA1**03, *DQB1**0302) will be excluded, since the KAN0009 peptide will not bind to this

MHC molecule. Patients who are positive for both HLA-DQ2.5 and HLA-DQ8 will be excluded due to the presence of the HLA-DQ8 allele.

Eligible patients are required to have maintained a self-reported GFD for at least 12 months prior to study enrollment, with negative (or weak positive) TTG and DGP antibodies at screening, to ensure proper adherence and experience with GFD during the study. Patients who have a history of hyperacute or prolonged symptomology (> 48 hours) following gluten exposure will be excluded from Part B to ensure the safety of patients exposed to the GC. Patients will remain on a GFD during the study with the exception of the mandated 3-day GC in Part B.

1.4. Determination of Starting Doses and Regimen

The planned doses of KAN-101 in this FIH study allow for a robust characterization of the safety and pharmacokinetics (PK) profile of KAN-101 encompassing the physiologically active doses identified in nonclinical models. The cumulative toxicology, safety pharmacology and PK data acquired from animal studies support dosing of KAN-101 in humans. A 4-week repeat-dose Good Laboratory Practice (GLP) toxicity study examining doses up to 74 mg/kg in Sprague-Dawley rats and cynomolgus monkeys demonstrated no significant findings in either species at any dose of KAN-101 examined. The no-observed-adverse-effect-level (NOAEL) was established as 74 mg/kg (the highest dose tested) from the GLP studies in both species.

In Part A (single ascending dose [SAD]), 4 escalating dose groups are planned: 0.15 mg/kg; 0.3 mg/kg; 0.6 mg/kg; and 1.2 mg/kg. These doses are supported by the NOAEL and include doses equivalent where effects were observed in nonclinical studies. The dosing schedule requires that successively higher doses will only be administered after the safety, tolerability and available PK data of the preceding dose group have been evaluated by the Safety Monitoring Committee (SMC) and approved by the Sponsor. Doses may be adjusted based on the PK and safety findings of the preceding dose group(s).

Part B will examine multiple doses (3) of KAN-101 and includes 3 escalating dose cohorts: 0.15 mg/kg; 0.3 mg/kg; and 0.6 mg/kg. During Part B, the doses of KAN-101 will be administered every 3 days. This frequency of dosing is supported by the nonclinical experimental autoimmune encephalomyelitis (EAE) mouse model that demonstrated that dosing every 3 days was more effective than weekly dosing.

For more information on the nonclinical findings, please see the KAN-101 Investigator's Brochure.

2. OBJECTIVES

2.1. Primary (Part A and Part B)

- Assess the safety and tolerability of escalating doses of KAN-101 in patients with CeD

2.2. Secondary (Part A and Part B)

- Assess the PK of KAN-101 after single and multiple doses of KAN-101 in patients with CeD

2.3. Exploratory (Part B only)

CC

3. ENDPOINTS

3.1. Primary Endpoint (Part A and Part B)

- Incidence and severity of treatment-emergent adverse events (TEAEs) as assessed by the Common Terminology Criteria for Adverse Events (CTCAE) v5.0 or higher

3.2. Secondary Endpoint (Part A and Part B)

- Plasma concentrations and PK parameters of KAN-101

3.3. Exploratory Endpoint (Part B only)

CCI

4. STUDY DESIGN

Study KAN-101-01 is a Phase 1, FIH study designed to evaluate the initial safety, tolerability, and activity of KAN-101 in patients with CeD on a GFD. An overview of the 2 parts and proposed dose groups is presented in [Figure 1](#).

4.1. PART A – Single Ascending Dose

Part A employs a SAD 3+3 design, in which patients will receive a single IV infusion of KAN-101 on Day 1 (D1) followed by 20 days of safety monitoring, which includes assessment of AEs, clinical signs and symptoms, and clinical laboratory values.

All cohorts in Part A will employ sentinel dosing, whereby the first patient in each cohort will be dosed at least 7 days prior to the subsequent patients to monitor for the acute and subacute safety of KAN-101. Based on nonclinical data, a sentinel period of 7 days should be sufficient to allow for complete drug clearance (>5 half-lives) and development of the immune tolerance mechanism.

The doses for Part A include 0.15 mg/kg (Cohort 1), 0.3 mg/kg (Cohort 2), 0.6 mg/kg (Cohort 3), and 1.2 mg/kg (Cohort 4). After the last patient within a given dose cohort has been followed for at least 7 days post-dose, a safety review will be performed by the SMC and will include review of all available safety and PK information. Dosing at the next dose level will only commence upon a recommendation from the SMC and approval by the Sponsor.

For all patients in Part A, the study will consist of a 28-day screening period, a single dose of KAN-101 administered on D1 and follow up through D21. D1 includes a 10-hour monitoring period in the clinic/hospital unit and a phone call follow up approximately 24 hours after dosing.

- If a patient is experiencing active AE(s) which require clinical monitoring at the end of the clinic/hospital unit monitoring period, the patient should not be discharged and should be followed until satisfactory resolution as determined by PI
- If feasible, patients should be advised to have someone stay with them after discharge until 24 hours have elapsed after study drug administration on D1.
- If patients do not live within 1-hour travel time of an emergency medical facility, they should remain in the clinic/hospital unit for the first 24 hours after study drug administration.
- Patients should be instructed not to drive themselves to seek emergency medical treatment.

Patients will be evaluated on D4 (± 1), D8, and D21. Blood and serum samples will be collected for PK and anti-drug antibody (ADA) assessments during Part A. Patients in Part A may be replaced if they do not receive the full dose of study drug or do not complete the D8 visit, as long as the discontinuation was not due to a DLT assessed to be related to study drug. In the event that patients are unable to return to the clinic for protocol-specified visits, alternative methods for

safety assessments and data collection may be employed to ensure the safety of the trial participant where appropriate.

Please see [Table 1](#) for the complete schedule of assessments for Part A.

4.2. PART B – Multiple Ascending Dose

Part B will be initiated following successful completion and SMC review of SAD Cohort 2 in Part A. This transition at Cohort 2 from single to multiple dosing of KAN-101 is supported by nonclinical models that show clearance of KAN-101 within 24 hours, and in vivo animal studies that did not show any drug accumulation when KAN-101 was given 3 times a week.

Part B employs a randomized, double-blind multiple ascending dose (MAD) design, in which 3 cohorts of patients will be assigned 3:1 to either KAN-101 or matching placebo (PBO). Patients in Part B will receive an IV infusion of KAN-101 or PBO on D1, D4, and D7. All cohorts in Part B will employ sentinel dosing, whereby the first 2 patients (1 KAN-101 and 1 PBO) in each cohort will be dosed at least 14 days prior to the subsequent patients (ie, 7 days following the third and final dose) to monitor for the acute and subacute safety of KAN-101.

The doses for Part B include 0.15 mg/kg (Cohort 5), 0.3 mg/kg (Cohort 6), and 0.6 mg/kg (Cohort 7). After the last patient dosed within a given cohort has been followed for at least 14 days, a safety review will be performed by the SMC. Initiation of the next dose cohort will commence upon recommendation by the SMC after review of available safety and PK data and approval of the Sponsor.

For all patients in Part B, the study will consist of a screening period of up to 28 days, followed by 3 doses of KAN-101, each administered on D1, D4, and D7. The first dose on D1 will be followed by a 10-hour monitoring period in the clinic/hospital unit and a phone call follow up approximately 24 hours after dosing. Subsequent doses scheduled on D4 and D7 have a 4-hour monitoring period in the clinic/hospital unit.

- If a patient is experiencing active AE(s) which require clinical monitoring at the end of the clinic/hospital unit monitoring period, the patient should not be discharged and should be followed until satisfactory resolution as determined by PI
- If feasible, patients should be advised to have someone stay with them after discharge until 24 hours have elapsed after study drug administration on D1.
- If patients do not live within 1-hour travel time of an emergency medical facility, they should remain in the clinic/hospital unit for the first 24 hours after study drug administration.
- Patients should be instructed not to drive themselves to seek emergency medical treatment.

Patients will return to the clinic on D15 to initiate oral GC and on D21 for biomarker sample collection. Blood and serum samples will be collected for PK, PD, and ADA assessments during Part B of the study. Patients in Part B may be replaced if they do not receive the full 3 doses of

study drug or do not complete the D21 visit, as long as the discontinuation was not due to a DLT assessed to be related to study drug. In the event that patients are unable to return to the clinic for protocol-specified visits, alternative methods for safety assessments and data collection may be employed to ensure the safety of the trial participant where appropriate.

To assess the PD effects of KAN-101, on D15 of Part B patients will begin a 3-day, self-administered high-dose (9 g of gluten protein) oral GC. Typically, a 3-day oral GC is not long enough to induce changes in GI histopathology, and reactions are limited to mild or moderate symptoms. Any severe symptoms experienced by patients during the GC will be treated as medically indicated. To ensure patient safety, patients with a history of hyperacute symptomology or prolonged symptoms after gluten exposure will be excluded from Part B.

The GC is positioned 1 week after the last dose to allow sufficient time for T cell tolerance induction to develop. The initial dose of the GC will be administered in the clinic, and patients will be monitored for at least 6 hours post gluten administration [REDACTED]. GC administration on D16 and D17 will be self-administered at home, at approximately the same time as the first in-clinic administration.

[figure not shown]
CCI

Based on data obtained during both the SAD and MAD parts of the study, the protocol may be amended to explore additional higher dose levels and dosing schedules if supported by the data, recommended by the SMC, and approved by the Sponsor.

Please see [Table 2](#) for the complete schedule of assessments for Part B.

Figure 1: Overview Study KAN-101-01

Single Ascending Dose (SAD): 3 patients will be dosed IV with KAN-101. Initiation of the next dose cohort will commence once all patients in a cohort reach D8 postdose, and upon acceptable safety review by SMC and approval from Sponsor.

Multiple Ascending Dose (MAD): the first MAD cohort will be initiated after safety review of SAD Cohort 2. Patients randomized 3:1 to KAN-101 or PBO. Initiation of the next dose cohort will commence once all patients in a cohort reach D15 postdose, and upon acceptable safety review by SMC and approval from the Sponsor.

All cohorts will employ sentinel dosing to allow for assessment of acute and subacute reactions prior to dosing additional patients in the study.

Abbreviations: CeD = celiac disease; IV = intravenous; n = number; PBO = placebo; SMC = safety monitoring committee.

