For all patients in Part A, the study will consist of a 28-day screening period, a single dose of KAN-101 administered on D1 followed by a 10-hour monitoring period in the clinic/hospital unit. Patients will be evaluated on D4 (± 1), D8, and D21. In the event that patients are unable to return to the clinic for protocol-specified visits, alternative methods for safety assessments and data collection may be employed to ensure the safety of the trial participant where appropriate. Blood and serum samples will be collected for PK and ADA assessments during the Part A.

Please see [Table 1](#) for the complete schedule of assessments for Part A.

Part B - MAD

Patients enrolled in the double-blind MAD part will be randomized 3:1 to KAN-101 or PBO administered IV for 3 doses. A total of 8 patients per dose cohort (6 KAN-101; 2 PBO) will be enrolled. All cohorts will employ sentinel dosing, whereby the first 2 patients (1 KAN-101 and 1 PBO) in each cohort will be dosed at least 14 days prior (ie, 7 days from third and final dose) to the subsequent patients being dosed to monitor for the acute and subacute safety of multiple doses of KAN-101.

The first MAD cohort (Cohort 5) will begin dosing after the safety review of the SAD Cohort 2 is completed. In Part B, the doses will be administered every 3 days, for a total of 3 doses, and the patients followed for approximately 28 days after the first dose. The planned Part B doses are 0.15 mg/kg, 0.3 mg/kg, and 0.6 mg/kg.

For all cohorts in Part B, after the last patient dosed within a given cohort has been followed for at least 14 days, a safety review will be performed by the SMC. Dosing in the next cohort will commence upon recommendation by the SMC and approval by the Sponsor.

A GC will be initiated on D15 to assess patients' T-cell response to gluten. For the GC, patients will self-administer 9 g of gluten protein orally (PO) on D15, D16, and D17, at approximately the same time each day. CCI

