4.7. Dose Escalation Safety Period

In Part A, the dose escalation safety monitoring period is from the beginning of IV administration through D8. Any AEs that meet the above criteria but occur after the dose escalation safety monitoring period of Part A may be considered by the SMC in the evaluation for Part B dose selection.

The dose escalation safety monitoring period in Part B is from the beginning of the first IV administration of KAN-101/PBO through the D15 clinic visit, prior to initiating the GC.

The length of the monitoring periods for safety review is supported by nonclinical exposure data, suggesting KAN-101 will have cleared 5 half-lives, and nonclinical animal model data demonstrating that the tolerance induction mechanism can develop within 1 week of dosing. AEs and any abnormal clinical parameters, including laboratory findings, observed during this period will be used by the SMC to determine whether dose escalation should proceed.

No patient with a DLT will be replaced.

In both parts, patients will be monitored in the clinic for 10 hours following the first IV administration of KAN-101/PBO. In Part B, patients will be monitored in the clinic for 4 hours following completion of their second and third dose.

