4.3 General Presentation Considerations and Descriptive Statistics

No formal statistical hypotheses or inferential statistics will be performed in this study. For Part A and Part B, summary statistics and listings will be provided by dose.

All by-visit summaries will be based on the nominal day/time per Appendix 6.1 [Table 8](#) (Part A) and [Table 9](#) (Part B) as recorded on the eCRF.

Study day will be calculated relative to the date of first dose, ‘Study Day’ = Assessment Date – First Dose Date + 1.

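### Part B sentinel interval: 14 days after dosing (D15) and 7 days after the third dose (D14) are stated as equivalent but differ by one day

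*Protocol*

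**What the plan says.** Protocol Section 4.2 states that the two Part B sentinels (one KAN-101, one placebo) "in each cohort will be dosed at least 14 days prior to the subsequent patients (ie, 7 days following the third and final dose". The synopsis, under Part B, has the same pair of intervals: the sentinels "will be dosed at least 14 days prior (ie, 7 days from third and final dose) to the subsequent patients being dosed". In both places the 7-day figure stands in parentheses after ie, as another way of saying 14 days.

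The dosing days are fixed: "Patients in Part B will receive an IV infusion of KAN-101 or PBO on D1, D4, and D7". Table 2 gives no visit window for D1, D4, D7 or D15.

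Protocol Section 10.7 and SAP Section 3.3 say only that the remaining six patients are randomised 5:1 once sentinel dosing is complete. SAP Section 3.1 mentions sentinel dosing without an interval. The synopsis and Section 4.2 are therefore the only places that say how long the Part B sentinels must be followed before the others are dosed.

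**The concern.** The stated purpose of the sentinel step is to observe acute and subacute safety over the full three-dose course before the rest of the cohort is exposed. The interval is the rule that a site applies to decide when the other patients may be dosed, and it is expressed from two starting points that lead to different calendar days.

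The gap is small but falls just before a visit. From D8 to D14 Table 2 schedules no safety labs, vital signs or ECG; all three are on D15. A site that counts from the third dose, in good faith and on the protocol's own words, could dose further patients one day before the sentinels' first scheduled labs and vital signs after their third infusion. Two sites, or two cohorts, could also apply different intervals without either noticing.

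**Working it through.** **Inputs**

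- Interval: 14 days, equated with 7 days after the third dose (Protocol synopsis and Section 4.2).
- Doses on D1, D4 and D7 (Protocol Section 4.2).
- Study-day rule: "Assessment Date – First Dose Date + 1" (SAP Section 4.3). The first dose is D1, so k elapsed days after study day s is D(s + k).
- Assessment days: Protocol Table 2.

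**Step 1. Test the stated equivalence.** The plan implies that 14 days from D1 and 7 days from D7 are the same day.

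| Counting convention | 14 days from D1 | 7 days from D7 | Gap |
|---|---|---|---|
| Elapsed days | 1 + 14 = D15 | 7 + 7 = D14 | 1 day |
| Inclusive (start day counts as day 1) | 1 + 14 − 1 = D14 | 7 + 7 − 1 = D13 | 1 day |
| Clear days (start and release days both excluded) | 1 + 14 + 1 = D16 | 7 + 7 + 1 = D15 | 1 day |

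The equivalence is not reproduced. A change of convention shifts both results equally, so the gap is always (1 + 14) − (7 + 7) = 1 day. The two agree only if one convention is used for the 14 days and another for the 7. Equivalently, D15 is 15 − 7 = 8 days after the third dose, and D14 is 14 − 1 = 13 days after the first.

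**Step 2. Find which convention the protocol uses.** In the notes to Figure 1, the 14-day follow-up in Part B becomes "Initiation of the next dose cohort will commence once all patients in a cohort reach D15 postdose", and the 7-day follow-up in Part A becomes "Initiation of the next dose cohort will commence once all patients in a cohort reach D8 postdose". Both are elapsed days: 1 + 14 = 15 and 1 + 7 = 8. On that convention the two sentinel expressions give D15 and D14.

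**Step 3. Compare with the Part B schedule (Table 2).**

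| Assessment | Scheduled, D1 onward | D8 to D14 | First after the D7 dosing day |
|---|---|---|---|
| Safety labs | D1, D4, D7 (all pre-dose), D15 | none | D15 |
| Vital signs | D1 (pre-dose), D15 | none | D15 |
| ECG | D1, D7 (before, during and 1 hour after infusion), D15 | none | D15 |

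The D7 labs are drawn before the third infusion and D7 has no scheduled vital signs, so D15 is the first scheduled occasion for either after the third infusion. For ECG the statement is narrower: D7 has a 1-hour post-infusion tracing, and D15 is the first after that day. Early-termination and unscheduled assessments are left out because they are contingent.

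**Step 4. Patients concerned.** Each cohort has 8 patients, so 8 − 2 sentinels = 6 remain. At 5:1 that is 5 on KAN-101 and 1 on placebo.

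**The case against.** The strongest reply is that the 14-day minimum governs. The parenthesis explains that minimum and does not create a second permission. Dosing others on D14 would be only 13 days after the sentinels' first dose and would breach the stated minimum, whereas D15 satisfies both expressions. This stands. A reader might infer that the protocol authorises release on D14; it does not. What remains is that the parenthesis, read alone, leads a site to D14.

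The protocol also counts loosely elsewhere. Section 4.2 places the gluten challenge one week after the last dose although D15 is 8 days after D7, and Section 4.10 puts D28 at about 20 days after the final dose when it is 28 − 7 = 21. The 7-day expression may therefore have been meant as D15. That is plausible and makes imprecise wording the likelier explanation than two competing rules. It does not settle the matter, because Figure 1 uses exact elapsed days.

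The sentinels are also not unobserved before D15. Their D4 and D7 pre-dose labs follow doses 1 and 2, D7 includes the 1-hour post-infusion ECG and 4 hours of observation, adverse events are monitored continuously, unscheduled tests are done when clinically indicated, and any DLT pauses enrolment. All of this stands. None of it is a scheduled lab or vital-sign assessment after the third infusion.

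Two further inferences are tempting. One is that the lost day removes a review of D15 results that would otherwise take place. No text makes dosing of the remaining patients depend on those results, and even with release on D15 they might not yet be back. The other is that release on D14 conflicts with the safety monitoring period, which "is from the beginning of the first IV administration of KAN-101/PBO through the D15 clinic visit, prior to initiating the GC". Section 4.7 uses that period for the decision to escalate between cohorts. It does not govern dosing within a cohort, so its closing on D15 contradicts nothing here.

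**Conclusion.** The equivalence stated in the synopsis and in Section 4.2 is arithmetically wrong by one day under any single counting convention. On the protocol's own convention the two expressions give D15 and D14. D15 meets both, so a site that applies the 14-day minimum is not misled; a site that counts from the third dose could release one day early. That day falls before the sentinels' first scheduled labs and vital signs after the third infusion, and before their first ECG after the D7 dosing day.

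The exposure is up to 6 patients per cohort, 5 on KAN-101, and only if the shorter count is used. A reader might multiply this to 3 × 6 = 18 of the 24 Part B patients. That is a ceiling: it needs every cohort to follow the parenthesis against the stated minimum, and nothing in the documents suggests that this would happen.

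The conclusion assumes dosing on exactly D1, D4 and D7, and takes the 14 days as running from the first dose, as the protocol's D15 usage implies. No endpoint or planned analysis is affected. The point is small, but it concerns a release rule in a first-in-human study and is worth correcting.

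**What to change.** Reconcile the synopsis (Part B) and Section 4.2 with each other and with the D15 visit in Table 2, so that both places give the same single study day and name the dose from which it is counted. Which of the two intervals is intended is for the sponsor to decide; this review does not choose between them.

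The cost is a wording change in two places in the Protocol. The SAP states no sentinel interval and needs no change. The two readings differ by one day per cohort, so any effect on timelines is limited to that.
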